3.0 OBJECTIVES

3.1 Study Objectives

3.1.1 Primary Objectives

- 1) To estimate the efficacy of repeated doses of LACTIN-V (2×10^9 cfu/dose) as compared to placebo in preventing BV recurrence by 12 weeks following treatment of BV with MetroGel
- 2) To assess the safety of LACTIN-V over 24 weeks by comparing the incidence of AEs between individuals randomized to LACTIN-V or placebo

3.1.2 Secondary Objectives

- 1) To investigate the colonization of LACTIN-V (presence of *L. crispatus* CTV-05 in the vaginal specimen) and fluctuations over 12 weeks, in relation to menses and sexual intercourse
- 2) To evaluate user acceptability and tolerability of LACTIN-V over 12 weeks, including perceptions around method of delivery and dosing
- 3) To measure long-term colonization of LACTIN-V at 24 weeks (12 weeks after last dosing)
- 4) To estimate the long-term efficacy of repeated doses of LACTIN-V (2×10^9 cfu/dose) as compared to placebo in preventing BV recurrence at 24 weeks (12 weeks after last dosing)

3.1.3 Exploratory Objective

To estimate the efficacy of repeated doses of LACTIN-V (2×10^9 cfu/dose) as compared to placebo in preventing repeated (more than one) episodes of BV recurrence up to 12 weeks following treatment of BV with MetroGel

3.2 Study Outcome Measures

3.2.1 Primary Efficacy Outcome Measure

The proportion of participants with a positive BV diagnosis in each study arm by Visit 4 (Week 12, Day 84)

BV recurrence is defined by Amsel criteria 3-4 and Nugent score 4-10. Following FDA draft guidance all BV diagnoses during follow-up visits are considered incident, as they occur at least 22-30 days after the commencement of MetroGel treatment and consequently are treatment failures or new infections [25]. For the purpose of this trial, treatment failure and new infection will both be considered recurrent BV.

3.2.2 Primary Safety Outcome Measure

The proportion of participants reporting product-related AEs and SAEs in each study arm through Visit 7 (Week 24, Day 168)

3.2.3 Secondary Efficacy Outcome Measures

Secondary Outcome Measure 1

The proportion of participants experiencing successful colonization with *L. crispatus* CTV-05 following dose of study product through Visit 4 (Week 12, Day 84) in the LACTIN-V arm, overall and by occurrence of menses and intercourse

Secondary Outcome Measure 2

The proportion of participants experiencing successful colonization with *L. crispatus* CTV-05 following dose of study product at Visit 7 (Week 24, Day 168) in the LACTIN-V arm, overall and by occurrence of menses and intercourse

Secondary Outcome Measure 3

Tolerability of LACTIN-V and the applicator will be measured by:

1. The proportion of participants who discontinue study product early in each study arm due to adverse events

Acceptability of LACTIN-V and the applicator will be measured by:

1. The proportion of participants who are compliant with the complete dose regimen in each study arm as assessed by participant reporting and applicator staining
2. Self-administered questionnaires about acceptability of the study product in each study arm

Secondary Outcome Measure 4

The proportion of participants with a positive BV diagnosis in each study arm by Visit 7 (Week 24, Day 168)

Exploratory Outcome Measure

The statistical parameterizations of the exploratory objective will include, but are not limited to, the following:

1. The number of BV recurrences per 12 weeks of follow-up
2. The probability of BV recurrence during the 12 weeks of follow-up

4.0 STUDY DESIGN

This is a Phase II-b multicenter randomized double-blind placebo-controlled trial to assess the efficacy of repeated doses of LACTIN-V compared to placebo in preventing BV recurrence in women diagnosed with BV. The study will also assess the safety of LACTIN-V by comparing the incidence of AEs between women randomized to LACTIN-V or placebo. The study plans to enroll 228 sexually-experienced, pre-menopausal women age 18 to 45 years. Women will be randomized 2:1 to receive LACTIN-V or placebo.

Women will be consented and will have a history and physical examination to include a pelvic exam with STI diagnostics and testing for BV. Potentially eligible women with Amsel criteria ≥ 3 will have a vaginal smear sent to a central laboratory for Gram stain evaluation by Nugent score. Blood will be obtained for HIV and syphilis serologies, a vaginal swab for gonorrhea, chlamydia and trichomonas molecular testing, and urine for β hCG. Potentially eligible women will start a standard 5-day course of MetroGel.

Women will return to the study clinic within 2 days after completing the 5-day course of MetroGel to re-evaluate eligibility criteria and review the BV test results from the screening visit. Women with Amsel criteria ≥ 3 and Nugent score 4-10 will be instructed to administer the LACTIN-V or placebo at home for 5 consecutive days and then twice weekly for 10 weeks. LACTIN-V (or placebo) will be administered at 2×10^9 cfu/dose by vaginal applicator.

Women will complete a memory aid to record times of product application, menses, sexual intercourse, concomitant medications, condom use and any AEs. Reminders will be sent to women in order to increase adherence with all doses and prior to scheduled follow-up visits. Women will complete either a paper or electronic memory aid. If the electronic version of the memory aid is utilized by the participant, the study clinic will be alerted of any potential AEs reported by the participant for follow-up and reporting as deemed necessary.

Follow-up visits are scheduled 4, 8, 12 and 24 weeks after enrollment. A memory aid to gauge symptoms and AEs will be reviewed, a questionnaire to collect clinical, including AEs, data will be administered and a pelvic exam will be performed to detect genital tract AEs. Vaginal swabs for wet mount evaluation (Amsel criteria) and Gram stain evaluation (Nugent score) will be collected. A vaginal swab for *L. crispatus* (including CTV-05) identification will be collected. Vaginal applicators will be collected at Visits 2, 3, and 4 and stained with Trypan Blue upon return to the site as a proxy for product use. Telephone interviews will be scheduled between the 12 and 24 week visits, at 16 and 20 weeks after enrollment.

5.0 STUDY ENROLLMENT AND WITHDRAWAL

The study plans to enroll 228 non-pregnant, pre-menopausal women age 18 to 45 years diagnosed with symptomatic or asymptomatic BV. Eligibility criteria for participation in the study are described in detail in sections 5.1 and 5.2. A screening consent form will be used for procedures to determine eligibility and an enrollment consent form will be used for study participation if eligibility is confirmed. Pregnant women, men and children are excluded from study participation (see section 14.4).

5.1 Subject Inclusion Criteria

Participants must meet all of the inclusion criteria in order to be eligible to participate in the study:

1. Capable of reading and writing English and voluntarily provide written informed consent to participate in the study and comply with all study procedures
2. Untreated BV (asymptomatic or symptomatic) as diagnosed during the screening visit defined by ≥ 3 Amsel criteria

Note: Amsel criteria include the following:

- Homogeneous, thin, grayish-white discharge that smoothly coats the vaginal walls;
 - Vaginal pH >4.5 ;
 - Positive whiff-amine test, defined as the presence of a fishy odor when a drop of 10% potassium hydroxide (KOH) is added to a sample of vaginal discharge;
 - Presence of clue cells ($>20\%$ on microscopy).
3. Untreated BV (asymptomatic or symptomatic) as confirmed in the laboratory using the Nugent scoring system (Nugent Score ≥ 4)
 4. Otherwise healthy pre-menopausal women 18–45 years of age on the day of screening
 5. Regular predictable menstrual cycles or amenorrheic for at least 3 months due to use of a long-acting progestin or continuous use of oral contraceptives
 6. Willing to be asked questions about personal medical health and sexual history
 7. Willing to apply study agent vaginally and comply with study examinations
 8. Agree to abstain from sexual intercourse during the first 5 consecutive days of study product administration, 12 hours prior to study visits and for 12 hours after each study product application
 9. Agree to abstain from the use of any other intravaginal product throughout the trial period from the time of screening through Visit 7 (Week 24, Day 168)

Note: Intravaginal products include contraceptive creams such as Gynol II, gels, foams, sponges, lubricants not approved by the study investigators, and douches. Limit use of tampons during menstruation to unscented products.

10. Must be of non-childbearing potential or if of childbearing potential, must agree to use a reliable method of birth control for the duration of the study

Note: Reliable methods of birth control include tubal ligation, male partner with a vasectomy, a steroidal contraceptive (oral, patch, injectable or implantable), IUD, condoms or abstinence.

5.2 Subject Exclusion Criteria

Participants meeting any of the following criteria at screening, or when assessed at the enrollment visit, will be excluded from the study:

1. Urogenital infection at screening
Note: Urogenital infection includes urinary tract infection, *Trichomonas (T.) vaginalis*, *Neisseria (N.) gonorrhoeae*, *Chlamydia (C.) trachomatis*, *Treponema (T.) pallidum*, or vulvo-vaginal candidiasis.
2. Diagnosis of two or more outbreaks of *N. gonorrhoeae*, *C. trachomatis*, *T. pallidum*, *T. vaginalis*, or herpes simplex virus (herpes genitalis) within 6 months prior to screening
3. Positive for syphilis or HIV at screening
4. Current pregnancy or within 2 months of last pregnancy and/or currently breastfeeding**
5. Vaginal or systemic antibiotic or antifungal therapy (other than MetroGel given as part of study procedures) within 21 days of screening or within 30 days of enrollment**
6. Use of disulfiram within past 2 weeks or other contraindication to use of MetroGel**
7. Any condition requiring regular periodic use of systemic antibiotics during participation in the trial
8. Active genital herpes lesion (if not resolved by enrollment)**
9. Investigational drug use other than LACTIN-V within 30 days or 10 half-lives of the drug, whichever is longer, of enrollment visit**
10. Other planned participation in an investigational drug study while participating in this study**
11. Menopause defined as more than 12 consecutive months of amenorrhea without another known cause including pregnancy
12. IUD insertion or removal, pelvic surgery, cervical cryotherapy or cervical laser treatment within the last 2 months prior to screening
13. Use of vaginal ring (eg, NuvaRing) within 3 days of screening or during the course of the study**
14. Failure to complete 5 days of MetroGel with the last dose taken no later than 48 hours prior to randomization***
15. Use of new long-acting hormonal treatments. Participant may be enrolled if stable (>3 months) on existing therapy as determined by the principal investigator**
16. Known allergy to any component of LACTIN-V/placebo or MetroGel or to nitroimidazole derivatives or latex (condoms)
17. Any social, medical, or psychiatric condition including history of drug or alcohol abuse that in the opinion of the investigator would make it unlikely for the participant to comply with the study

** Note: Criteria will be assessed at screening and enrollment.

*** Note: Criteria will be assessed at enrollment.

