NIAID	National Institute of Allergy and Infectious Diseases, NIH, DHHS
NIH	National Institutes of Health
OCRA	Office of Clinical Research Affairs, DMID, NIAID, NIH, DHHS

OHRP	Office for Human Research Protections
ORA	Office of Regulatory Affairs, DMID, NIAID, NIH, DHHS
OSEL	Office of Science and Engineering Laboratories
pH	Potential Hydrogen
PI	Principal Investigator
PP	Per Protocol
qPCR	Quantitative Polymerase Chain Reaction
RR	Rate Ratio
rUTI	Recurrent Urinary Tract Infection
SAE	Serious Adverse Event
SDCC	Statistical and Data Coordinating Center
SMC	Safety Monitoring Committee
SOP	Standard Operating Procedure
STAR	Sexually Transmitted Infections Treatment and Research
STI	Sexually Transmitted Infection
STI-CTG	Sexually Transmitted Infections Clinical Trials Group
US	United States
UTI	Urinary Tract Infection

PROTOCOL SUMMARY

Title:	Phase II-b Randomized Double-Blind Placebo-Controlled Trial of Lactobacillus crispatus CTV-05 (LACTIN-V) to Prevent the Recurrence of Bacterial Vaginosis
Phase:	II-b
Population:	228 non-pregnant, pre-menopausal women age 18 to 45 years diagnosed with bacterial vaginosis (BV)
Number of Sites:	Four U.S. sites
Study Duration:	72 weeks after enrollment of the first participant
Participant Participation Duration:	24 weeks per participant
Description of Agent:	Lactobacillus (L.) crispatus CTV-05 (LACTIN-V) contains a naturally occurring vaginal strain of L. crispatus CTV-05, preserved as a powder applied by a vaginal applicator. LACTIN-V at 2×10^9 cfu/dose or matching placebo will be administered by vaginal applicator once daily for 5 consecutive days, followed by twice weekly for 10 consecutive additional weeks.
Primary Objectives	
1) To estimate the efficacy of repeated doses of LACTIN-V (2×10^9 cfu/dose) as compared to placebo in preventing BV recurrence by 12 weeks following treatment of BV with MetroGel vaginal gel (MetroGel)2) To assess the safety of LACTIN-V over 24 weeks by comparing the incidence of AEs between individuals randomized to LACTIN-V or placebo

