CTV-05 is a strain of *L. crispatus*, a gram-positive rod isolated from the vagina of a healthy woman. *L. crispatus* is found naturally in the vaginas of healthy women and is commonly found as a component of the natural human intestinal flora. It is a facultative anaerobe, homofermentor of lactic acid, fastidious in its growth, and capable of H₂O₂ production. Unlike most commercially available strains of *Lactobacillus*, CTV-05 adheres well to vaginal epithelial cells and is capable of colonizing the vaginal epithelium.

LACTIN-V administered as a capsule has been tested in four trials (LV 001-004) with a dose level up to 5×10^8 cfu/capsule. Since the dose of 5×10^8 cfu/capsule resulted in colonization rates lower than desired, several changes to the study product were made. The higher dose of 2×10^9 cfu/dose delivered via vaginal applicator as dried powder directly into the upper vaginal vault has been tested in a Phase 1 trial (LV-005) in 12 healthy women and subsequently in a Phase II-a trial (LV-006) in 24 women with BV.

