2.2 Rationale

This Phase II-b trial is designed to provide a screening evaluation for the hypothesis that, following a 5-day course of MetroGel to treat BV, LACTIN-V administered at 2×10^9 cfu/dose using a vaginal applicator reduces the 12-week incidence of BV recurrence by

≥50% when compared to placebo. Based on the achieved colonization rate of *L. crispatus* CTV-05 at 2×10^9 cfu/dose of LACTIN-V, coupled with prior data from the Phase II-a clinical trial suggesting that vaginal colonization with *L. crispatus* CTV-05 was associated with a reduced risk of BV recurrence, the next logical step is to perform a larger Phase II-b trial.

We plan to enroll 228 women in a 2:1 ratio of LACTIN-V to placebo to estimate the effectiveness of 2×10^9 cfu/dose of LACTIN-V to prevent the recurrence of BV following standard antibiotic treatment with MetroGel and establish longer term safety and acceptability data up to 24 weeks.

The study will be conducted at domestic sites with a known track record of recruiting participants in other BV studies to enable enrollment of all 228 women over 48 weeks. This will allow the study to complete study follow up 18 months after the first woman enrolls in the trial. This timeline assumes that all sites initiate enrollment at about the same time.

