4.4.5. Prior and Concomitant Therapy

The following drugs and procedures are prohibited during the specified time periods as they may affect efficacy assessments:

- Vaginal or systemic antibiotic or antifungal therapy (other than MetroGel given as part of study procedures) within 21 days of screening or within 30 days of enrollment;
- Use of new long-acting hormonal treatments;
- Investigational drug use other than LACTIN-V within 30 days or 10 half-lives of the drug;
- Use of disulfiram within past 2 weeks or other contraindication to use of MetroGel;
- IUD insertion or removal, pelvic surgery, cervical cryotherapy or cervical laser treatment within the last 2 months prior to screening
- Use of vaginal ring (eg, NuvaRing) within 3 days of screening or during the course of the study.

Prior to unblinding, a blinded case review committee will review subjects with a reported concomitant infection/disease/procedure that may interfere with study product, use of concomitant medications or products that may interfere with study product, significant protocol deviations, and other events that may impact study product effectiveness or study analyses.

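### Exclusion criterion 9 exempts LACTIN-V from the pre-entry washout and no other rule bars prior exposure, so a woman already carrying CTV-05 could count as colonized in the placebo arm

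*Protocol*

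**What the plan says.** Protocol 5.2, item 9, excludes for "Investigational drug use other than LACTIN-V within 30 days or 10 half-lives of the drug, whichever is longer, of enrollment visit" and is marked for assessment at both screening and enrollment. SAP 4.3 repeats it. SAP 4.4.5 lists "Investigational drug use other than LACTIN-V within 30 days or 10 half-lives of the drug" among therapies prohibited because they could influence the efficacy assessments.

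The neighbouring rules cover other situations:

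- Exclusion 10, "Other planned participation in an investigational drug study while participating in this study", concerns concurrent studies, not earlier ones.
- Inclusion 9, "Agree to abstain from the use of any other intravaginal product throughout the trial period from the time of screening through Visit 7", starts at screening.
- Rescreening (Protocol 5.3.3.1 and 7.1.1) is for women screened out before randomization.
- Protocol 5.3.4 says that randomized women are not replaced. It does not address re-entry.
- Protocol 6.5 documents medications only from 30 days before screening, so older exposure need not appear in the medication record.

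On the analysis side, SAP 3.3.3 defines successful colonization as CTV-05 and *L. crispatus* both above their detection limits, with no condition on the baseline value. SAP 8.2 tests LACTIN-V against placebo on colonization at any post-baseline time through Visit 4 (Table 21), at Visit 7 (Table 22) and by visit (Tables 23-26).

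**The concern.** The criterion is applied before the first dose, so a first-time participant does not need the exemption. Read literally, it lets in women recently exposed to the test strain itself. Since no other rule mentions prior LACTIN-V use, women with older exposure are admitted as well.

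The protocol treats persistence as a live question. One secondary objective is "To measure long-term colonization of LACTIN-V at 24 weeks (12 weeks after last dosing", and Protocol 2.1 reports 42% colonization after 4 months in the ITT cohort of the earlier capsule trial.

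Three things are at stake. A carrier on placebo raises placebo colonization and so narrows the SAP's between-arm contrast. If she is also protected, placebo recurrence moves towards the active arm. And a woman randomized twice would contribute two correlated records to chi-square tests that assume independent ones.

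**Working it through.** **1. The plan's own figure.** Inputs from Protocol 11.4: placebo recurrence 0.30, LACTIN-V 0.15 (a 50% reduction), 2:1 allocation, 70% power, 10% dropout. Protocol 11.3 gives a two-sided 5% Pearson chi-square test. With pooled proportion (0.30 + 2 × 0.15)/3 = 0.20, the placebo-arm size is

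n = [1.960 × √(1.5 × 0.20 × 0.80) + 0.524 × √(0.30 × 0.70 + 0.15 × 0.85/2)]² / 0.15² ≈ 67.7, rounded up to 68.

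The total is 3 × 68 = 204, and 204/0.90 = 226.7, so 227 against the stated 228. Power at 228 × 0.90 = 205.2 evaluable women is 70.4%. The figure reproduces, and none of its inputs depends on criterion 9.

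**2. What the exemption itself changes.** Dosing ends in Week 11 (Protocol 6.2), that is by about Day 77. Visit 7 falls on Days 161-175. The shortest gap is 161 − 77 = 84 days, about 12 weeks. A woman who completed this trial therefore clears a 30-day washout with or without the exemption. The documents give no half-life for the live organism, so the 10-half-life limb cannot be shown to catch her. The exemption matters for recent exposure. For older exposure, the gap is the missing exclusion.

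**3. Whether re-entry is possible in time.** Enrollment is planned "to enable enrollment of all 228 women over 48 weeks" and participation is "24 weeks per participant". Assuming uniform accrual, 228 × 24/48 = 114 women are enrolled by week 24, of whom 114 × 2/3 = 76 are on LACTIN-V. This is an upper bound on the pool, not a forecast. Women enrolled near week 24 would have no time left to rescreen and complete MetroGel.

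**4. An illustration.** The placebo arm is 228/3 = 76 women. Suppose 4 are carriers with the LACTIN-V risk of 15%.

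- Placebo recurrence: (72 × 0.30 + 4 × 0.15)/76 = 22.2/76 = 29.2%, against 30%.
- Placebo colonization: up by 4/76 = 5.3 points, if all four are CTV-05-positive at a post-baseline visit.

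**5. Sensitivity of the primary test.** Let f be the share of placebo women who are protected carriers; the documents give no value. The placebo rate becomes 0.30(1 − f) + 0.15f, with LACTIN-V held at 0.15 and 205.2 evaluable women.

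| f | Placebo rate | Power |
|---|---|---|
| 0 | 30.0% | 70.4% |
| 1% | 29.85% | 69.7% |
| 2% | 29.7% | 68.9% |
| 5% | 29.25% | 66.6% |
| 10% | 28.5% | 62.5% |

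The example in step 4 (f = 5.3%) lies close to the 5% row.

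**The case against.** The strongest reply is that the scenario is remote. A re-entrant must again have BV (Amsel at least 3, Nugent at least 4) and then complete MetroGel. In the capsule trial, colonized women had fewer symptomatic recurrences (12.5% against 36%), so women who qualify again are likely to be mostly non-carriers. The four-carrier example is also generous. At 2:1, four on placebo imply about 12 carrier re-entrants. If 42% of re-entrants carried the strain, that means 12/0.42 ≈ 29 former LACTIN-V women out of a pool of at most 76. All of this stands, and it keeps the likely size small.

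The exemption may also be a drafting slip. Protocol 6.5 exempts the study product from its on-study list of prohibited drugs, where an exemption makes sense. That may explain how the wording arose, but it does not alter what the pre-dose criterion says.

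The plan has partial safeguards. The blinded case review committee (SAP 6.3.2.5) may censor or remove women case by case, and the mock-ups of Tables 23-30 show a Day 1 row. However, no stated criterion directs the committee to prior exposure, and no planned analysis removes or adjusts for Day 1 positives.

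A reader might infer that the exemption is what lets completers of this trial back in. Step 2 shows that it is not. A reader might also infer that the plan permits double randomization. It is only silent: it speaks of 228 women, and the Manual of Procedures, which is not among the documents, may forbid re-entry.

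**Conclusion.** The gap is real on the text: the pre-dose washout exempts the test product, and nothing else bars prior LACTIN-V exposure or a second randomization. The more exposed result is the SAP's between-arm colonization comparison, at about 1.3 points (1/76) per placebo carrier. The protocol's own colonization outcomes (Protocol 3.2.3) are defined within the LACTIN-V arm, so placebo carriage does not directly alter them. The expected effect on the primary test is small: about 0.8 points of placebo recurrence in the example. A trial planned at 70% power has little to spare, but only an f of 5% or more would cost several points of power.

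These sizes assume that carriers have the full LACTIN-V benefit and that f takes the values shown; the true frequency is unknown and likely low. It would go too far to say that prior exposure always dilutes the effect. Two thirds of re-entrants would draw LACTIN-V, and women who relapse may have a higher baseline risk in either arm. This is a cheap improvement, not a flaw that undermines the trial.

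**What to change.** Remove the LACTIN-V exemption from Protocol 5.2 item 9 and from SAP 4.3 and 4.4.5. Deletion alone is not enough (step 2), so also add an exclusion such as: *any previous receipt of LACTIN-V or its placebo in a clinical trial, including previous randomization in this trial*. Naming the placebo means that nobody has to be unblinded to judge eligibility.

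SAP 4.1 records that a third of the planned women had already completed Visit 2 by the DSMB meeting of June 2017. If enrollment is too advanced to amend, state in the SAP that only each woman's first randomization is analysed, and repeat Tables 11 and 21 without women who are CTV-05-positive on the Visit 1 qPCR. Protocol 7.2 already collects that swab, ahead of randomization and the first dose in its list of procedures, so the restriction uses a baseline measurement and applies equally to both arms.

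The cost is the loss of a few previously exposed candidates and one extra sensitivity analysis. The sample size stays at 228.
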